13.3 POWER CALCULATIONS

Power calculations were simulation-based. The following model was used for the simulations:

$$\logtitre_{t=2} = b_0 + b_{baseline} \logtitre_{t=1} + b_{priorvax} priorvax + b_C vax_C + b_R vax_R + b_{C-add} vax_C priorvax + b_{R-add} vax_R priorvax + e$$

The following table contains the interpretation of all model terms.

Term	Interpretation
logtitre _{t=2}	Post-vaccination log-titre.
b ₀	Expected post-vaccination log-titre for baseline log-titre 0, infrequent prior vaccination, vaccinated with QIV-E.

b_{baseline}	Expected increase in the post-vaccination log-titre for a 1-unit increase in the pre-vaccination log-titre. Adjusted for prior vaccination frequency and vaccine received.
$\log\text{titre}_{t=1}$	Pre-vaccination log-titre.
b_{priorvax}	Expected difference in the post-vaccination log-titre between the frequently and infrequently vaccinated. Adjusted for baseline titre.
priorvax	0=Infrequent prior vaccinations. 1=Frequent prior vaccinations and vaccine received.
b_C	Expected difference in post-vaccination log-titre between QIV-E and QIV-C. Adjusted for baseline titre and prior vaccination frequency.
vax_C	0=Not vaccinated with QIV-C. 1=Vaccinated with QIV-C.
b_R	Expected difference in post-vaccination log-titre between QIV-E and QIV-R vaccine. Adjusted for baseline titre and prior vaccination frequency.
vax_R	0=Not vaccinated with QIV-R. 1=Vaccinated with QIV-R.
$b_{C\text{-add}}$	Expected additional effect of QIV-C in the frequently vaccinated.
$b_{R\text{-add}}$	Expected additional effect of QIV-R in the frequently vaccinated.
e	Random error

The following table contains the values used for the parameters in the model (subsequent tables will show deviations if there are any).

Term	Value
b_0	1.1
b_{baseline}	0.8
b_{priorvax}	-0.2
b_C	0.25
b_R	0.5
$b_{C\text{-add}}$	0
$b_{R\text{-add}}$	0.2

In each simulation there was an equal number of subjects in each arm and vaccination history group. Baseline log-titres were simulated from $N(3.7, 1)$ which produced a distribution representative of the baseline titre data of published studies. The error term was sampled from $N(0, 1)$ which produces post-vaccination titre distribution representative of published studies.

The model simulates a subject's post-vaccination titre given their pre-vaccination titre, prior vaccination status (frequent or infrequent) and the vaccine they were given (QIV-R, QIV-C, QIV-E). The effect of the vaccines was allowed to vary between frequently and infrequently vaccinated.

Simulations were performed with different per-group sample sizes and different effects of QIV-R (b_R). For the purposes of fitting the model to the simulated data, all titres were censored to the appropriate interval (<10, 10-20, 20-40 up to 5260-10240 on the original titre scale) to simulate real measurements. The model was then fit using the midpoints of the intervals except <10 which was censored to 5 (as it would be for real data).

There were 5000 simulations for each sample size and value of b_R . Each simulated dataset was used to fit a model (the same one that was used to simulate it). The primary outcome measure was taken to be the effect of the QIV-R as compared to the QIV-E (i.e., the expected difference in post-vaccination log-titres between the QIV-R and QIV-E,) which corresponds to the b_R parameter in the model. A one-sided and a two-sided test was performed on the b_R estimate for each simulation. The "power" is the proportion of simulated studies that showed that b_R is significantly greater than 0. The results are in the table below.

Per-arm per-vaccine history sample size	True b_R (expected ratio between QIV-R and QIV-E)	Proportion with significant (one-sided) positive b_R	Proportion with significant (two-sided) positive b_R
50	0.5 (1.65)	0.772	0.665
55	0.5 (1.65)	0.810	0.712
60	0.5 (1.65)	0.832	0.741
70	0.5 (1.65)	0.889	0.807
80	0.5 (1.65)	0.920	0.858
200	0.25 (1.28)	0.775	0.676
220	0.25 (1.28)	0.810	0.717
240	0.25 (1.28)	0.834	0.742

Power of 80% can be achieved (for a one-sided test) with approximately 55 subjects per arm/per vaccine history given the true effect of 0.5 (true expected ratio 1.65). The total sample required would be approximately 330 subjects. This equates to 74% power for a two-sided test.

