6 OBJECTIVES AND OUTCOMES

6.1 PRIMARY OBJECTIVE

To assess whether vaccination with recombinant quadrivalent influenza vaccine (QIV-R) results in a better antibody response against A(H3N2) viruses than either standard egg-grown vaccine (QIV-E) or cell-based vaccines (QIV-C) as measured by post-vaccination geometric mean titre from the haemagglutination inhibition assay.

Corresponding outcome measures:

1. Post vaccination GMT in each vaccination group, adjusted for vaccination history and baseline titre.
2. Difference in log-titres between the QIV-R and QIV-E, adjusted for vaccination history and baseline titre.
3. Difference in log-titres between the QIV-R and QIV-C, adjusted for vaccination history and baseline titre.

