13.2 SAMPLE SIZE ESTIMATION & JUSTIFICATION

The sample size is calculated considering the primary objective to test whether QIV-R offers superior immunogenicity independent of vaccination history. Our estimates for post-vaccination HI titres are based on a study among elderly adults in Hong Kong, comparing QIV-R and QIV-E (20) and is similar to the estimated sample size based on similar HI titres in a study of 18-49 year olds (21).

A sample was simulated under the following model, informed by the published estimates:

$$titre_{t=2} = titre_{t=1} + vax_R + vax_C + priorvax + vax_R \times priorvax + vax_C \times priorvax$$

(titre_{t=2} = post vaccination log titre; titre_{t=1} = post-vaccination log titre for QIV-E infrequent vaccination; vax_R = QIV-R vaccinated; vax_C = QIV-C vaccinated)

For the test of a superior A(H3N2) response among vaccinees receiving QIV-R versus QIV-E or QIV-C (one-sided test for the parameter vax_{recomb}) and assuming $\alpha=0.05$, $\beta=0.2$, the sample needed to test these effects is around 55 per arm per vaccination history. Accounting for 10% attrition, the target sample for recruitment will be 60 per arm per vaccination history.

	Infrequently vaccinated	Frequently vaccinated	Total
QIV-R	60	60	120
QIV-E	60	60	120
QIV-C	60	60	120
Total	180	180	360

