13.4 STATISTICAL ANALYSES

Study Name: Immunogenicity trial of 3 influenza vaccine [VAP3]

Protocol Number: 2021.247

DSRB Ref Number: 2022/00275

Version & date: version 2.0, dated 27 Oct 2022

Page 31 of 38

The stratification variable of vaccination history will be included as a covariate in models for all primary and secondary objectives.

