13.4.1 PRIMARY OBJECTIVE

To assess whether vaccination with recombinant quadrivalent influenza vaccine (QIV-R) results in a better antibody response against A(H3N2) viruses than either standard egg-grown vaccine (QIV-E) or cell-based vaccine (QIV-C) as measured by post-vaccination geometric mean titre from the haemagglutination inhibition assay

Post-vaccination GMTs will be calculated for each group using the model described in 13.3, in which the outcome is an individual's post-vaccination titre, estimated given their pre-vaccination titre, prior vaccination status (frequent or infrequent) and the vaccine they were given (QIV-R, QIV-C, QIV-E). A t-test (on a model parameter) will be used to assess statistical significance of the effects of QIV-R versus QIV-E and QIV-C.

13.4.2 SECONDARY OBJECTIVE 1

To estimate whether antibody responses to all 4 vaccine antigens are greatest in participants who received QIV-R and least in participants who received QIV-E, and if this reflects greater cell- to egg-grown antibody titre ratios.

The post-vaccination vs pre-vaccination **log-titre difference** (geometric mean ratio) will be compared using linear regression with the explanatory variable being the type of vaccine (reference QIV-E, separate parameter for QIV-R and QIC-C). A t-test will be used to assess statistical significance of the effects of QIV-R and QIC-C (as compared to reference) as well as the difference in those effects.

The post-vaccination **seropositivity** (coded as 1 if the post-vaccination titre is at least 40, 0 otherwise) will be compared using logistic regression with the explanatory variable being the type of vaccine (reference QIV-E, separate parameter for QIV-R and QIC-C). A t-test will be used to assess statistical significance of the effects of QIV-R and QIC-C (as compared to reference) as well as the difference in those effects.

Seroconversion (coded as 1 if the post/pre vaccination titre ratio is at least 4, 0 otherwise) will be compared using logistic regression with the explanatory variable being the type of vaccine (reference QIV-E, separate parameter for QIV-R and QIC-C). A t-test will be used to assess statistical significance of the effects of QIV-R and QIC-C (as compared to reference) as well as the difference in those effects.

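### The parameter that section 13.3 powers as the primary effect, b_R, is the QIV-R v QIV-E effect in infrequently vaccinated participants only; the overall contrasts the primary objective needs are never defined

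*Combined protocol and SAP*

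**What the plan says.** - **Objective.** Section 6.1 lists as a primary outcome measure "Difference in log-titres between the QIV-R and QIV-E, adjusted for vaccination history and baseline titre", with a parallel item for QIV-R v QIV-C. Section 13.2 says the trial is sized "to test whether QIV-R offers superior immunogenicity independent of vaccination history".
- **Model.** Section 13.3 regresses post-vaccination log-titre on baseline log-titre, priorvax (0 infrequent, 1 frequent), vax_C, vax_R and both vaccine-by-priorvax products. Its table of terms describes b_R as "Expected difference in post-vaccination log-titre between QIV-E and QIV-R vaccine. Adjusted for baseline titre and prior vaccination frequency" and b_R-add as "Expected additional effect of QIV-R in the frequently vaccinated". The planning values are b_R = 0.5, b_R-add = 0.2, b_C = 0.25 and b_C-add = 0.
- **Parameter powered.** Section 13.3 takes the primary outcome measure to be the QIV-R v QIV-E effect, "which corresponds to the b_R parameter in the model", and its power table covers b_R alone. Section 13.2 applies a single QIV-R parameter to both comparators: "response among vaccinees receiving QIV-R versus QIV-E or QIV-C (one-sided test for the parameter", followed by the name of that parameter.
- **Analysis.** Section 13.4.1 points back to the 13.3 model and adds: "A t-test (on a model parameter) will be used to assess statistical significance of the effects of QIV-R versus QIV-E and QIV-C". The general statement in 13.4 is "The stratification variable of vaccination history will be included as a covariate in models for all primary and secondary objectives". Section 13.4.4 brings in the interaction as an addition for Secondary objective 3.

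**The concern.** Once a 0/1 history indicator is multiplied by the vaccine indicators, the coefficient on vax_R no longer averages over history. It is the vaccine difference in the stratum coded 0. The two descriptions in the table of terms therefore conflict: if b_R-add is extra effect in the frequently vaccinated, b_R cannot be an effect adjusted across both groups.

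Three things follow.

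1. The only parameter the plan identifies does not answer 6.1 or 13.2, and the frequently vaccinated half of the sample adds almost nothing to its estimate. That is the half in which the plan assumes the larger QIV-R effect.
2. Section 13.4.1 leaves the parameter unnamed. An analyst could defend b_R, a stratum average or a fit without interactions. These differ in meaning or power, and the choice could be made after the data are seen.
3. QIV-R v QIV-C is part of the primary objective, has the smaller assumed effect, and has no reported power.

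**Working it through.** **What the model implies.** Setting priorvax to 0 and then 1 in the 13.3 equation:

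| Contrast | Infrequent | Frequent | Equal-weight average |
|---|---|---|---|
| QIV-R − QIV-E | b_R = 0.5 | b_R + b_R-add = 0.7 | b_R + 0.5·b_R-add = 0.6 |
| QIV-R − QIV-C | b_R − b_C = 0.25 | (b_R − b_C) + (b_R-add − b_C-add) = 0.45 | (b_R − b_C) + 0.5·(b_R-add − b_C-add) = 0.35 |

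**Reproducing the plan's table.** The inputs are those of 13.3: baseline N(3.7, 1), error N(0, 1), the coefficients listed there, titres grouped into doubling intervals and set to midpoints, and values below 10 set to 5. Each data set was fitted by least squares with both interactions (10,000 runs per setting). As in the plan, the two-sided column counts significant positive results.

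| Per cell | b_R, rebuilt (one-/two-sided) | b_R, plan |
|---|---|---|
| 50 | 0.772/0.666 | 0.772/0.665 |
| 55 | 0.803/0.704 | 0.810/0.712 |
| 60 | 0.837/0.745 | 0.832/0.741 |
| 70 | 0.886/0.810 | 0.889/0.807 |
| 80 | 0.916/0.856 | 0.920/0.858 |

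A second, independent simulation also agreed with every row of the plan's table to within 2 percentage points, including the b_R = 0.25 rows.

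**The table is a one-stratum comparison.** With 55 v 55 in one stratum and residual SD 1, SE = √(2/55) = 0.191. Power is about Φ(0.5/0.191 − 1.645) = 0.836 one-sided. Rounding the titres raises the SE to about 0.200, giving Φ(2.5 − 1.645) = 0.804, close to the plan's 0.810. In 4,000 simulated trials the mean SE of b_R was 0.199 using all 330 participants and 0.200 using only the 165 infrequently vaccinated. The two estimates correlated at 0.998.

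**Power of the candidate contrasts at 55 per cell.** The averaged contrast has SE 0.200/√2 = 0.141. The normal approximation is Φ(effect/SE − z), with z = 1.645 or 1.96.

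| Contrast | Effect | SE | Approximation | Simulation (one-/two-sided) |
|---|---|---|---|---|
| QIV-R v QIV-E, b_R | 0.50 | 0.200 | 0.804/0.705 | 0.803/0.704 |
| QIV-R v QIV-E, average | 0.60 | 0.141 | 0.995/0.989 | 0.995/0.989 |
| QIV-R v QIV-C, b_R − b_C | 0.25 | 0.200 | 0.346/0.239 | 0.348/0.238 |
| QIV-R v QIV-C, average | 0.35 | 0.141 | 0.799/0.699 | 0.802/0.704 |

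At 60 per cell the averaged QIV-R v QIV-C contrast has 0.825/0.734.

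**Sensitivity to b_R-add.** If b_R-add = 0, the averages at 55 per cell have 0.969/0.941 (v QIV-E) and 0.564/0.430 (v QIV-C).

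**Illustrative cases for QIV-R v QIV-E** (not taken from the plan):

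| Where QIV-R works | b_R | Average |
|---|---|---|
| Frequent only, 0.7 | 0.048/0.025 | 0.802/0.699 |
| Frequent only, 0.5 | 0.048/0.023 | 0.552/0.429 |
| Infrequent only, 0.5 | 0.810/0.712 | 0.561/0.431 |

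In the first two rows b_R is truly zero, so its rejection rate is simply the nominal level.

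**Type I error.** With all vaccine effects set to zero, every contrast rejects 5.0–5.5% of the time one-sided.

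**The case against.** The best defence is that the trial was sized on the weaker stratum on purpose. Section 13.2 gives numbers per arm per vaccination history, and the lay summary (4.1) wants the best vaccine identified in both history groups. On the planning values the infrequently vaccinated have the smaller effect, so adequate power there implies more in the frequently vaccinated (about 0.97 one-sided). But no section states this intent, and the table of terms describes b_R as adjusted for history rather than specific to a stratum.

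Other points carry some weight:

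- Section 13.4.2 does specify models without interactions and a test of the QIV-R v QIV-C difference. Those are for fold-rise, seropositivity and seroconversion under a secondary objective, not the primary analysis.
- Section 6.1 names both comparisons in words. Adjusting for history does not fix a contrast once the effect may differ by history.
- Calling history a covariate does not exclude an interaction, and 13.4.4 concerns the secondary analyses. Neither flatly contradicts 13.3; they only leave the primary model less clear.
- Section 4.2.1 says the study is powered primarily against QIV-E. That explains why QIV-C power is missing, but 6.1 and 13.4.1 keep QIV-C in the primary objective, and 13.2 claims its sample size for both comparators.
- For QIV-R v QIV-E a reader can follow 13.3 to b_R. The room for choice after the fact is greatest for QIV-R v QIV-C.
- Equal weights are one choice. In the simulations a model without interactions gave practically the same power.

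**Conclusion.** The concern holds. The parameter that 13.3 treats as primary is the QIV-R v QIV-E effect in infrequently vaccinated participants, whereas 6.1 and 13.2 ask about QIV-R across vaccination histories, and no section defines that overall contrast for either comparator.

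For QIV-R v QIV-E the sample size is not at risk: under the plan's values the averaged contrast has over 98% power even two-sided. What is at fault is which question is tested, and that half the sample goes almost unused if b_R is tested. For QIV-R v QIV-C the definition decides whether the comparison is adequately powered: about 80% one-sided for the average, about 35% for b_R − b_C. A two-sided 5% test of the averages reaches 80% power only against QIV-E, at either 55 or 60 per cell.

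These figures rest on the plan's own coefficients, unit residual SD and equal cells. The 80% for QIV-R v QIV-C also depends on b_R-add = 0.2; with b_R-add = 0 it falls to 56% one-sided. Because this settles what the primary test means, it should be corrected before any outcome data are analysed by arm.

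**What to change.** 1. In 13.3 and 13.4.1, pre-specify the primary contrasts as averages over the two randomisation strata: b_R + 0.5·b_R-add for QIV-R v QIV-E, and (b_R − b_C) + 0.5·(b_R-add − b_C-add) for QIV-R v QIV-C. Coding priorvax as −0.5/+0.5 is equivalent and makes b_R and b_R − b_C these averages directly.
2. If 0/1 coding stays, correct the descriptions of b_R and b_C to say that they apply to the infrequently vaccinated.
3. Restate power for both averaged contrasts, one-sided and two-sided.
4. Keep the interaction tests for Secondary objective 3.
5. If a stratum-specific effect is really meant to be primary, say so, reword 6.1 and 13.2, and give power for each stratum.
6. While editing, align the synopsis, which names a mixed-effects regression for the primary analysis, with the model in 13.3.

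The cost is wording, one stated contrast per comparison and a rerun of the existing simulation, with no added participants. The trade-off is that averaging loses power if QIV-R works only in the infrequently vaccinated (0.56 against 0.81 one-sided for a 0.5 benefit). The average is still the question that 6.1 and 13.2 pose, and differences by stratum are examined under Secondary objective 3.

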12.4 REPLACEMENTS

The sample recruited allows for some attrition. However, we will attempt to replace participants who fail to attend their first follow-up (V2).

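### Section 13.3 states 74% two-sided power for about 55 per cell (330 in total), but its own table gives 71.2%; 74.1% is the row for 60 per cell.

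*Combined protocol and SAP*

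**What the plan says.** Section 13.2 sizes the trial on a one-sided test of the QIV-R effect with alpha 0.05 and beta 0.2. It arrives at about 55 per arm per vaccination history and then enlarges this: "Accounting for 10% attrition, the target sample for recruitment will be 60 per arm per vaccination history".

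Section 13.3 reports the simulations behind that number. On sidedness it says: "A one-sided and a two-sided test was performed on the b_R estimate for each simulation". On precision it says: "There were 5000 simulations for each sample size" and value of b_R. For a true b_R of 0.5 (ratio 1.65), the relevant table rows are:

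| Per cell | One-sided | Two-sided |
|---|---|---|
| 50 | 0.772 | 0.665 |
| 55 | 0.810 | 0.712 |
| 60 | 0.832 | 0.741 |

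The text under the table says that 80% one-sided power needs about 55 per cell. It continues: "The total sample required would be approximately 330 subjects". The next and last sentence is: "This equates to 74% power for a two-sided test".

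Section 13.4.1 describes the primary test: "A t-test (on a model parameter) will be used to assess statistical significance of the effects of QIV-R versus QIV-E and QIV-C". It does not say whether the test is one-sided or two-sided.

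**The concern.** The word with which the closing sentence opens can refer only to the sample just named, 55 per cell or 330 in total. For that sample the table shows 71.2%, not 74%. The prose thus contradicts the table it summarises, and it is the only place in the text where two-sided power is put into words.

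A reader who takes the primary test to be two-sided, which section 13.4.1 leaves possible, would carry away 74% as the planned power. At stake is the accuracy of a stated operating characteristic, not the size of the trial.

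**Working it through.** **Inputs (sections 13.2 and 13.3).** Alpha 0.05; b_R 0.5; residual SD 1; baseline log-titre mean 3.7, SD 1; equal cells; titres grouped in two-fold intervals and fitted at midpoints, with values below 10 set to 5; 5000 runs per setting; 10% attrition; 60 recruited per cell.

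**1. Lookup.** There are 3 arms × 2 history groups = 6 cells. 6 × 55 = 330, the total named in the text, and its row gives 0.712 two-sided. 6 × 60 = 360, and its row gives 0.741. The stated 74% matches the second row. Against the first, the difference is 0.74 − 0.712 = 0.028.

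**2. Does the table reproduce?** The section 13.3 model was simulated again with the stated parameters and titre grouping. Natural logs were assumed, which fits exp(0.5) = 1.65. With 5000 runs and arithmetic midpoints:

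| Per cell | Table, one-/two-sided | Rerun, one-/two-sided |
|---|---|---|
| 50 | 77.2% / 66.5% | 77.8% / 67.1% |
| 55 | 81.0% / 71.2% | 80.9% / 70.9% |
| 60 | 83.2% / 74.1% | 83.2% / 74.2% |
| 70 | 88.9% / 80.7% | 87.8% / 79.9% |
| 80 | 92.0% / 85.8% | 91.4% / 85.3% |

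Log-scale midpoints give 71.4% two-sided at 55 and 74.6% at 60. A larger rerun (20,000 per setting, both midpoint choices) gives 70.3–70.6% at 55 and 74.7% at 60. The table is sound.

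**3. Do the table's two columns agree with each other?** In a normal approximation, two-sided power = Φ(z₁ + 1.645 − 1.960), where z₁ is the normal quantile of the one-sided power.

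- 55 per cell: z₁ for 0.810 is 0.878, so Φ(0.563) = 0.713 (table 0.712).
- 60 per cell: z₁ for 0.832 is 0.962, so Φ(0.647) = 0.741 (table 0.741).
- Exactly 80% one-sided: z₁ = 0.842, so Φ(0.527) = 0.701.

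So 80–81% one-sided corresponds to 70–71% two-sided. A two-sided power of 74% goes with about 83% one-sided.

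**4. Simulation noise.** The standard error of 0.712 at 5000 runs is √(0.712 × 0.288 / 5000) = 0.0064, with 95% interval 0.699 to 0.725. As a fixed value, 0.74 lies 0.028 / 0.0064 = 4.4 standard errors above. If 74% came from a second run of 5000, the standard error of the difference is √(0.712 × 0.288 / 5000 + 0.74 × 0.26 / 5000) = 0.0089, and the gap is 3.1 standard errors. Allowing for rounding up from 73.5% leaves about 2.6.

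**5. A different method.** Without titre grouping, two-sided power at 55 would be 73.4% by simulation. A plain two-group normal approximation gives 74.6%: the standard error is √(2/55) = 0.191, 0.5 / 0.191 = 2.62, and Φ(2.62 − 1.96) = 0.746. But section 13.3 says titres were grouped, and the same approximation gives 83.6% one-sided at 55 against the table's 81.0%. It is not the plan's method.

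**6. Could 74% mean the 360 recruited?** That needs 60 analysed per cell. With the planned attrition, 60 × 0.9 = 54 remain. The larger rerun gives 80.0–80.1% one-sided and 70.1–70.3% two-sided at 54.

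**7. Size.** The risk of missing a true b_R of 0.5 is 1 − 0.712 = 0.288, against 1 − 0.74 = 0.26 as stated.

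**The case against.** The strongest reply is that 74% is a genuine figure from the plan: it is the row for the recruitment target, and the author probably quoted the power for planned enrolment without saying so. That is a likely origin, and on that reading the defect is an unlabelled denominator. It does not rescue the sentence. The closing text of section 13.3 mentions neither 60 per cell nor 360, and section 13.2 recruits 60 precisely because it expects losses. Section 12.4 promises only an attempt at replacing those who miss V2. Replacement could restore 60 analysed per cell, but the plan does not count on it.

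A second reply is that two-sided power is supplementary, since section 13.2 states a one-sided test. This stands, and it limits the weight of the point. The silence on sidedness in section 13.4.1 makes the two-sided figure relevant but is a separate matter.

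A third is that the 4.4 standard errors treat 74% as exact. That is fair: the more cautious figures are 3.1 and 2.6. Noise remains an unlikely explanation, and the table lookup settles the matter without it.

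**Conclusion.** The concern holds. At the sample it names, the closing sentence of section 13.3 overstates two-sided power by 2.8 percentage points: 74% stated, 71.2% in the table. The lookup rests on no assumption; only the confirming reruns assume natural logs and a choice of midpoint, and their results barely depend on the latter.

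The consequence is small. The table is right, the one-sided 80% at about 55 per cell stands, and no sample size changes.

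The 71% applies to b_R alone, which in the model with interaction terms is the QIV-R versus QIV-E difference among the infrequently vaccinated. It must not be read as the power for the contrast averaged over both history groups. Under the plan's own parameters that contrast is 0.5 + 0.5 × 0.2 = 0.6, and the reruns put its two-sided power at about 99% with 54–55 per cell.

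**What to change.** Replace the last sentence of section 13.3 with wording such as:

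> With 55 analysed per arm per vaccination history (about 330 in total), power for a two-sided test of b_R is 71%; it is 74% only with 60 analysed per arm per vaccination history (360 in total).

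Optionally, add that 10% attrition from 60 leaves 54 per cell, with about 80% one-sided and 70% two-sided power for b_R. The cost is one corrected sentence, with no extra participants and no change to design or analysis.
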